4. STUDY OBJECTIVES

4.1 Primary Objective

To investigate the safety and tolerability of a single dose of LY3832479 in healthy participants.

The primary endpoints are serious and non-serious adverse events (AE), laboratory measures of safety, electrocardiogram (ECG), and vital signs.

4.2 Secondary Objective

To characterize the PK of LY3832479 following a single intravenous (IV) administration of LY3832479 to healthy participants.

The secondary endpoints are area under the concentration versus time curve (AUC) and maximum observed drug concentration (C_{max}).

5. STUDY DESIGN

Study PGAA is a Phase 1, randomized, placebo-controlled study of LY3832479 administered to healthy participants. A study schema for PGAA can be seen in [Figure 1](#).

The study will comprise up to 3 cohorts:

Cohorts 1 and 2 (at least 9 participants):

[figure not shown]
- 7 randomized to LY3832479 and
- 2 randomized to placebo.

Cohort 3 (at least 8 participants):

- 6 randomized to LY3832479 and
- 2 randomized to placebo.

A maximum of 30 participants will be enrolled to study intervention such that approximately 8 participants have sufficient evaluable data in each cohort.

After at least 7 participants have completed Day 4 in a given cohort, all safety data up to this cutoff date will be reviewed to determine whether the next cohort can be dosed, as well as the dose to be used, after agreement between the Lilly's medical monitor and the investigator. Safety and tolerability data will be the primary criteria guiding dose-escalation.

Abbreviations: LY = LY3832479; PBO = placebo.

Figure 1: A general schema for study J2Z-MC-PGAA

6. TREATMENTS

The following is a list of the study treatment abbreviations that will be used in the TFLs.

Cohort	Study Treatment Name	Treatment order in TFL
All	Pooled placebo IV	1
1	700 mg LY3832479 IV	2
2	2800 mg LY3832479 IV	3
3	7000 mg LY3832479 IV	4

7. SAMPLE SIZE JUSTIFICATION

A maximum of 30 participants will be enrolled to study intervention such that approximately 8 participants have sufficient evaluable data in each cohort.

The sample size not powered on the basis of statistical hypothesis testing. However, the number of subjects is common in early clinical pharmacology studies and is considered sufficient to achieve the objectives of the trial.

8. DEFINITION OF ANALYSIS POPULATIONS

The “Entered” population will consist of all participants who sign the informed consent form (ICF).

The “Safety” population will consist of all participants randomly assigned to study intervention (LY3832479 or placebo) and who are administered at least 1 dose of study intervention.

The “Pharmacokinetic” population will consist of all randomized participants who received study intervention (LY3832479), have baseline, and have multiple evaluable PK samples.

All protocol deviations that occur during the study will be considered for their severity/impact and will be taken into consideration when subjects are assigned to analysis populations.

9. STATISTICAL METHODOLOGY

9.1 General

Data listings will be provided for all data that are databased. Summary statistics and statistical analysis will only be presented for data where detailed in this SAP. For continuous data, summary statistics will include the arithmetic mean, arithmetic standard deviation (SD), median, minimum, maximum, and N; for log-normal data (e.g. the PK parameters: AUCs and C_{max}) the geometric mean and geometric coefficient of variation (CV%) will also be presented. For categorical data, frequency count and percentages will be presented. Data listings will be provided for all subjects up to the point of withdrawal, with any subjects excluded from the relevant population highlighted. Summary statistics and statistical analyses will generally only be performed for subjects included in the relevant analysis population. For the calculation of summary statistics and statistical analysis, unrounded data will be used.

Mean change from baseline is the mean of all individual subjects' change from baseline values. Each individual change from baseline will be calculated by subtracting the individual subject's baseline value from the value at the timepoint. The individual subject's change from baseline values will be used to calculate the mean change from baseline using a SAS procedure such as Proc Univariate.

Data analysis will be performed using SAS® Version 9.4 or greater.

9.2 Demographics and Subject Disposition

Subject disposition will be summarized and listed. The demographic variables age, sex, race, ethnicity, body weight, height and body mass index will be summarized and listed. All other demographic variables will be listed only.

9.3 Pharmacokinetic Assessment

Venous blood samples will be collected as specified in the protocol's schedule of assessments for determination of concentrations of serum LY3832479 used to evaluate the PK of LY3832479.

9.3.1 Pharmacokinetic analysis

Any PK analyses prior to database lock will be the responsibility of Eli Lilly PK/PD group, whereas any PK analyses post database lock will be reported by Covance.

Noncompartmental methods applied with a validated software program (Phoenix WinNonlin Version 8.1 or later) to the serum concentrations of LY3832479 will be used to determine the following PK parameters, when possible:

Parameter	Units ^a	Definition
AUC(0-t _{last})	µg.h/mL	Area under the concentration versus time curve from time zero to time t, where t is the last time point with a measurable concentration
AUC(0-∞)	µg.h/mL	Area under the concentration versus time curve from time zero to infinity
%AUC(t _{last} -∞)	%	Percentage of AUC(0-∞) extrapolated
C _{max}	µg/mL	Maximum observed drug concentration
t _{last}	h	Time of the last observed drug concentration
t _{max}	h	Time of maximum observed drug concentration
t _½	h	Half-life associated with the terminal rate constant (λ_z) in non-compartmental analysis
CL	L/h	Total body clearance of drug calculated
V _z	L	Volume of distribution during the terminal phase
V _{ss}	L	Volume of distribution at steady state

^aSerum LY3832479 drug concentration units will come in from the bioanalytical lab as ng/mL to one decimal place; the data will be transformed to µg/mL for analysis.

Additional PK parameters may be calculated, as appropriate.

The software and version used for the final analyses will be specified in the CSR. Any exceptions or special handling of data will be clearly documented within the final study report.

Formatting of tables, figures and abbreviations will follow the Eli Lilly Global PK/PD/TS Tool: NON-COMPARTMENTAL PHARMACOKINETIC STYLE GUIDE. The version of the tool effective at the time of PK analysis will be followed.

General PK Parameter Rules

- Actual sampling times will be used in the final analyses of individual PK parameters, except for non-bolus pre-dose sampling times which will be set to zero.
- C_{max} and time of maximum observed drug concentration (t_{max}) will be reported from observed values. If C_{max} occurs at more than one time point, t_{max} will be assigned to the first occurrence of C_{max} .
- AUC parameters will be calculated using a combination of the linear and logarithmic trapezoidal methods (linear-log trapezoidal rule). The linear trapezoidal method will be applied up to t_{max} and then the logarithmic trapezoidal method will be used after t_{max} . The minimum requirement for the calculation of AUC will be the inclusion of at least three consecutive serum concentrations above the lower limit of quantification, with at least one of these concentrations following C_{max} .
- AUC(0- ∞) values where the percentage of the total area extrapolated is more than 20% will be flagged. Any AUC(0- ∞) value excluded from summary statistics will be noted in the footnote of the summary table.
- Half-life ($t_{1/2}$) will be calculated, when appropriate, based on the apparent terminal log-linear portion of the concentration-time curve. The start of the terminal elimination phase for each subject will be defined by visual inspection and generally will be the first point at which there is no systematic deviation from the log-linear decline in serum concentrations. Half-life will only be calculated when a reliable estimate for this parameter can be obtained comprising of at least 3 data points. If $t_{1/2}$ is estimated over a time window of less than 2 half-lives, the values will be flagged in the data listings. Any $t_{1/2}$ value excluded from summary statistics will be documented in the footnote of the summary table.
- A uniform weighting scheme will be used in the regression analysis of the terminal log-linear portion of the concentration-time curve.
- The parameters based on predicted last quantifiable drug concentration will be reported (except in bioequivalence and bioavailability studies, where only the observed parameters will be reported).

Individual PK Parameter Rules

- Only quantifiable concentrations will be used to calculate PK parameters with the exception of special handling of certain concentrations reported below the lower limit of quantification (BQL). Serum concentrations reported as BQL will be set to a value of zero when all of the following conditions are met:
 - The compound is non-endogenous.
 - The samples are from the initial dose period for a subject or from a subsequent dose period following a suitable wash-out period.
 - The time points occur before the first quantifiable concentration.
- All other BQL concentrations that do not meet the above criteria will be set to missing.
- Also, where two or more consecutive concentrations are BQL towards the end of a profile, the profile will be deemed to have terminated and therefore any further quantifiable concentrations will be set to missing for the calculation of the PK parameters unless it is considered to be a true characteristic of the profile of the drug.

Individual Concentration vs. Time Profiles

- Individual concentrations will be plotted utilizing actual sampling times.
- The terminal point selections will be indicated on a semi-logarithmic plot.

Average Concentration vs. Time Profiles

- The average concentration profiles will be graphed using scheduled (nominal) sampling times.
- The average concentration profiles will be graphed using arithmetic average concentrations.
- The pre-dose average concentration for single-dose data from non-endogenous compounds will be set to zero. Otherwise, only quantifiable concentrations will be used to calculate average concentrations.
- Concentrations at a sampling time exceeding the sampling time window specified in the protocol, or $\pm 10\%$, will be excluded from the average concentration profiles.
- Concentrations excluded from the mean calculation will be documented in the final study report.

- A concentration average will be plotted for a given sampling time only if 2/3 of the individual data at the time point have quantifiable measurements that are within the sampling time window specified in the protocol or $\pm 10\%$. An average concentration estimated with less than 2/3 but more than 3 data points may be displayed on the mean concentration plot if determined to be appropriate and will be documented within the final study report.

Treatment of Outliers during Pharmacokinetic Analysis

Application of this procedure to all PK analyses is not a requirement. Rather, this procedure provides justification for exclusion of data when scientifically appropriate. This procedure describes the methodology for identifying an individual value as an outlier for potential exclusion, but does not require that the value be excluded from analysis. The following methodology will not be used to exclude complete profiles from analysis.

Data within an Individual Profile

A value within an individual profile may be excluded from analysis if any of the following criteria are met:

- For PK profiles during multiple dosing, the concentration of the pre-dose sample exceeds all measured concentrations for that individual in the subsequent post-dose samples.
- For PK profiles during single dosing of non-endogenous compounds, the concentration in a pre-dose sample is quantifiable.
- For any questionable datum that does not satisfy the above criteria, the profile will be evaluated and results reported with and without the suspected datum.

Data between Individual Profiles

1. If $n < 6$, then the dataset is too small to conduct a reliable range test. Data will be analyzed with and without the atypical value, and both sets of results will be reported.
2. If $n \geq 6$, then an objective outlier test will be used to compare the atypical value to other values included in that calculation:
 - a. Transform all values in the calculation to the logarithmic domain.
 - b. Find the most extreme value from the arithmetic mean of the log transformed values and exclude that value from the dataset.
 - c. Calculate the lower and upper bounds of the range defined by the arithmetic mean $\pm 3*SD$ of the remaining log-transformed values.
 - d. If the extreme value is within the range of arithmetic mean $\pm 3*SD$, then it is not an outlier and will be retained in the dataset.

e. If the extreme value is outside the range of arithmetic mean $\pm 3*SD$, then it is an outlier and will be excluded from analysis.

If the remaining dataset contains another atypical datum suspected to be an outlier and $n \geq 6$ following the exclusion, then repeat step 2 above. This evaluation may be repeated as many times as necessary, excluding only one suspected outlier in each iteration, until all data remaining in the dataset fall within the range of arithmetic mean $\pm 3*SD$ of the log-transformed values.

Reporting of Excluded Values

Individual values excluded as outliers will be documented in the final report. Approval of the final report will connote approval of the exclusion.

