9.3.2 Pharmacokinetic statistical methodology

All PK parameters will be summarized by treatment using descriptive statistics.

The PK parameter estimates will be evaluated to delineate dose proportionality. Log-transformed C_{max} , and $AUC(0-\infty)$ of LY3832479 will be evaluated using a power model (where log-dose acts as an explanatory variable) to estimate ratios of dose-normalized geometric means and corresponding 90% confidence intervals. In addition, results of the dose proportionality will be plotted.

The estimated ratio of dose-normalized geometric means of PK parameters between the highest and lowest doses will be used to assess dose proportionality.

Example SAS code for the analysis:

```
proc mixed data=pk;
  model log_pk = log_dose / alpha=0.1 cl solution residual ddfm=kr;
  estimate '700 mg' intercept 1 log_dose 2.87506126 / alpha=0.1 cl; /*Log of 700 */
  estimate '2800 mg' intercept 1 log_dose 3.44715803 / alpha=0.1 cl; /*Log of 2800 */
  estimate '7000 mg' intercept 1 log_dose 3.84509804 / alpha=0.1 cl; /*Log of 7000 */
  estimate '2800 mg - 250 mg' log_dose 0.97003679 / alpha=0.1 cl; /*Difference in
  log values of 7000 and 700 */
  ods output solutionf=est;
  ods output estimates=estims;
run;
```

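### SAP 9.3.1 both requires and does not require dropping a flagged PK value, and at 6–7 per cohort its 3-SD test, if run on every cohort, flags a valid value in 27–31% of clean cohorts

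*SAP*

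**What the plan says.** SAP 9.3.1 has a sub-section on outliers in the PK analysis. Its opening paragraph makes the procedure optional: it "provides justification for exclusion of data when scientifically appropriate", and it "does not require that the value be excluded from analysis".

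The rules for comparing values between participants follow.

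- **Step 1, n < 6:** "then the dataset is too small to conduct a reliable range test". The remedy is: "Data will be analyzed with and without the atypical value, and both sets of results will be reported".
- **Step 2, n ≥ 6:** take logs, set aside the value furthest from the mean, and compute the mean ± 3 SD of the rest. If the set-aside value is outside that range, "then it is an outlier and will be excluded from analysis" (step 2e). The test may be repeated while at least 6 values remain.

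For n ≥ 6 no reporting with and without the value is planned. Excluded values are documented in the report, and "Approval of the final report will connote approval of the exclusion".

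SAP section 5 plans 7 active participants in each of Cohorts 1 and 2, and for Cohort 3 "6 randomized to LY3832479 and" 2 to placebo. Every full cohort therefore falls under step 2. SAP 9.3.2 then fits a power model to log Cmax and log AUC(0-∞) "to estimate ratios of dose-normalized geometric means and corresponding 90% confidence intervals".

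**The concern.** Two instructions in one section conflict. An analyst who keeps a flagged value and one who drops it can both claim to follow the SAP, and the choice would be made after the data are seen.

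The cut at n = 6 also looks arbitrary. Step 1 concedes that a range test is unreliable with 5 values, yet at n = 6 the SD itself rests on 5 values. An SD from so few values is often too small by chance, so 3 of them is not a demanding limit.

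If valid values are dropped, the geometric CV% is understated and the power-model intervals, the only confidence intervals planned for PK, become too narrow.

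**Working it through.** The documents give no false-flag rate, so there is no planned figure to reproduce.

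**Inputs from the documents.** Active cohorts of 7, 7 and 6 (SAP section 5; cohort sizes are minimums). Doses of 700, 2800 and 7000 mg (SAP section 6). The rule in steps 2a–2e. Log-normal AUC and Cmax (SAP 9.1).

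**Assumptions not in the documents.** Independent values with no true outliers; sample SD; the test applied within each dose group; CVs of 20–40%; and, for screened use, a value counts as atypical if it is 1.5-fold or 2-fold from the mean of the rest.

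**1. Flag rate per clean cohort.** For a set-aside value, (value − mean of rest) / (SD of rest × √(1 + 1/(n−1))) follows a t distribution with n−2 degrees of freedom. Hence

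P(flag) = 2n × P(t with n−2 df > 3/√(1 + 1/(n−1))).

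- n = 6: 3/√1.2 = 2.739 on 4 df, so 12 × 0.0260 = 0.312.
- n = 7: 3/√(7/6) = 2.777 on 5 df, so 14 × 0.0195 = 0.273.

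| n | 5 | 6 | 7 | 8 | 9 | 10 |
|---|---|---|---|---|---|---|
| Formula | 0.374 | 0.312 | 0.273 | 0.247 | 0.229 | 0.216 |
| Simulation, 400,000 sets each | 0.372 | 0.312 | 0.273 | 0.248 | 0.229 | 0.216 |

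The rate falls smoothly and nothing changes at 6. A 5% rate would need about 5.3 SD at n = 6 or 4.7 SD at n = 7.

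**2. Whole trial, one parameter.** 1 − (1 − 0.273)² × (1 − 0.312) = 0.636. With two parameters, simulation gives 84–87% for correlations from 0.8 down to 0.

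**3. If only values that look atypical are tested.** Chance of at least one flag across the 7/7/6 cohorts:

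| CV | 1.5-fold screen | 2-fold screen |
|---|---|---|
| 20% | 0.374 | 0.020 |
| 30% | 0.576 | 0.257 |
| 40% | 0.618 | 0.466 |

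**4. Effect on spread.** When the flagged value is dropped, a flagged cohort's log SD falls to a median 0.56 (n = 6) or 0.60 (n = 7) of its full value.

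**5. Effect on the power model.** The ratio of dose-normalised means between top and bottom dose is (7000/700)^(slope − 1), so its interval covers exactly when the slope's interval does. With all values kept, the natural-log doses 6.551, 7.937 and 8.854 (weights 7, 7, 6) have mean 7.727. The sum of squares is 7(1.176²) + 7(0.210²) + 6(1.127²) = 17.6, so the slope's SD is σ/√17.6 = 0.238σ. Simulation (40,000 trials, one pass, every flagged value dropped) gives:

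| | All values kept | Flagged values dropped |
|---|---|---|
| Coverage of 90% CI, all trials | 0.900 | 0.838 |
| Coverage, trials with an exclusion | 0.900 | 0.802 |
| Slope SD | 0.238σ | 0.262σ |
| Mean CI half-width, relative | 1 | 0.936 |

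The interval narrows by 6% while the slope's true SD rises by 10% (0.262/0.238 = 1.10). The slope stays unbiased. A run of 200,000 trials gave coverage 0.839 against 0.900 and a half-width ratio of 0.937.

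**6. Screened use, flagged values dropped.** Overall coverage is 0.855 (1.5-fold) and 0.897 (2-fold) at CV 20%, and 0.839 and 0.865 at CV 30%. In trials with an exclusion it is 0.780–0.806, against 0.903–0.974 for the same trials with all values kept.

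**The case against.** - **The test is not meant for every cohort.** The opening paragraph says so, and step 2 speaks of an atypical value. This stands: 27–31% and 64% are upper bounds. The SAP does not define atypical, however, so no actual rate can be derived, and step 2b simply takes the most extreme value.
- **The opening paragraph may govern.** Step 2e could describe only what follows once the team chooses to apply the test. That is a possible reading, but the text does not state it.
- **A cohort-level flag need not reach the power model.** The test refers to the values in a given calculation, and the power model pools about 20 values. This is a real assumption behind the coverage figures. Step 2e's exclusion is unqualified, so carrying it into the model is a fair reading. The effect on CV% does not depend on it.
- **Coverage among trials with an exclusion can mislead.** At CV 20% with the 2-fold screen only 2% of trials have an exclusion, and overall coverage is 0.897, almost no loss. The 200,000-trial run confirms the conditional figures there (0.79 against 0.97), but they describe a rare event.
- **Exclusions are visible and little depends on them.** They are documented, databased data are listed, and whole profiles cannot be removed this way. PK is secondary and descriptive, the study is unpowered, and no dose-proportionality limit is set. All true, and it limits the importance of the point. But a reader would have to recompute the untrimmed result.
- **Changing will to may in step 2e, plus reporting both ways, would be enough.** That removes the contradiction but still leaves the main analysis to be chosen after the data are seen.

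**Conclusion.** The point holds. The SAP contradicts itself on whether a flagged value leaves the main analysis, and its with-and-without safeguard stops just below the planned cohort sizes, although the test is hardly more reliable at 6 or 7 than at 5.

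The size depends on use. If the test is run on every cohort and every flag is acted on, about 64% of trials lose at least one valid value per parameter, and the 90% power-model interval covers about 84%. With screening at CV 20–30%, overall coverage is 84–90%. If no flagged value is dropped, the effect is zero. These figures assume clean log-normal data, dose-group testing, and exclusions carried into the power model; the CVs and screens are assumptions.

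The primary safety objective is untouched. This should be corrected before the PK analysis, but it does not threaten the trial.

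**What to change.** Amend SAP 9.3.1 in three ways:

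1. Keep all values in the main PK summaries and the power model; a 3-SD flag alone does not remove a value.
2. Extend step 1's reporting with and without the atypical value to n ≥ 6, which covers every cohort here. The SAP already reports both ways for questionable points within a profile.
3. Reconcile step 2e with the opening paragraph, for example: *is flagged as a potential outlier; the main analysis keeps it, and results without it are also reported*.

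This bars exclusion on the flag alone. If the team wants to keep a route for exclusion on documented scientific grounds, the SAP should state it separately.

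The cost is SAP wording, one extra set of PK summaries when a value is flagged, and possibly somewhat wider reported CV% and intervals.

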9.3.2 Pharmacokinetic statistical methodology

All PK parameters will be summarized by treatment using descriptive statistics.

The PK parameter estimates will be evaluated to delineate dose proportionality. Log-transformed C_{max} , and $AUC(0-\infty)$ of LY3832479 will be evaluated using a power model (where log-dose acts as an explanatory variable) to estimate ratios of dose-normalized geometric means and corresponding 90% confidence intervals. In addition, results of the dose proportionality will be plotted.

The estimated ratio of dose-normalized geometric means of PK parameters between the highest and lowest doses will be used to assess dose proportionality.

Example SAS code for the analysis:

```
proc mixed data=pk;
  model log_pk = log_dose / alpha=0.1 cl solution residual ddfm=kr;
  estimate '700 mg' intercept 1 log_dose 2.87506126 / alpha=0.1 cl; /*Log of 700 */
  estimate '2800 mg' intercept 1 log_dose 3.44715803 / alpha=0.1 cl; /*Log of 2800 */
  estimate '7000 mg' intercept 1 log_dose 3.84509804 / alpha=0.1 cl; /*Log of 7000 */
  estimate '2800 mg - 250 mg' log_dose 0.97003679 / alpha=0.1 cl; /*Difference in
  log values of 7000 and 700 */
  ods output solutionf=est;
  ods output estimates=estims;
run;
```

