- LY3832479 is a mAb directed against a foreign target and was isolated from a convalescent patient with COVID-19. Therefore, the test article does not bind to antigens/targets expressed in human tissues as confirmed by a GLP-complaint TCR study in human tissues, representing a low risk for potential on-target or off-target toxicity.
- The 1x exposure-based margin for 7000 mg is based on the maximum dose tested in monkeys in the single-dose toxicology/TK study. Based on clinical observations and gross examination at necropsy, no toxicity was observed in the animals administered 186 mg/kg of LY3832479 (final report pending).
- The risk of infusion-related reaction is considered low due to the target, the reduced effector function (Fc and Complement binding), and the human origin of this antibody.
- The engineered LALA mutations are expected to reduce Fc effector function in LY3832479 and should reduce the risk of ADE (see [Section 2.2](#)).

Table 4.1. Margin of Safety for Intravenous Administration of LY3832479 Based on Administered Dose and Predicted Exposure

	Dose (mg/kg)	Dose Multiple ^a	AUC _{0-∞} (mg*h/mL) ^a	AUC Exposure Multiple ^a	Cmax (mg/mL)	Cmax Exposure Multiple ^a
Starting human dose^b	10	18.6	75	~10	0.253	~19
Highest human dose^b	100	1.86	753	~1.0	2.51	~1.9
Cynomolgus monkey maximum tested dose^c	186		750		4.75	

Abbreviations: AUC = area under the concentration versus time curve; AUC_{0-∞} = AUC from time zero to infinity; Cmax = maximum drug concentration; NOAEL = no-observed-adverse-effect level.

^a Dose multiple is the dose in animals/dose in humans based on milligrams per kilogram. Exposure multiple is the calculated AUC and Cmax in animals and predicted AUC and Cmax in humans.

^b Assume 70-kg bodyweight.

^c Maximum tested dose in the single-dose monkey toxicology/toxicokinetic study.

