6.1. Study Interventions Administered

Intervention Name	LY3832479	Placebo
Type	Biologic	Not applicable
Dose Formulation	Solution for infusion	0.9% sodium chloride solution
Unit Dose Strength(s)	400-mg vial	Placebo
Dosage Level(s)	
 • Cohort 1: 700 mg • Cohort 2: 2800 mg • Cohort 3: 7000 mg 	Not applicable
Route of Administration	IV infusion	IV infusion
Use	Experimental	Placebo
IMP and NIMP	IMP	IMP
Sourcing	Provided by Lilly	Provided by site
Packaging and Labeling	Provided in glass vials and labeled appropriately	Per site procedure

Abbreviations: IMP = investigational medicinal product; IV = intravenous; NIMP = noninvestigational medicinal product.

This following table describes the infusion volume and rate for LY3832479. Placebo volume and rate will match the LY3832479 dose cohort.

The infusion rate may be reduced as deemed necessary if an infusion reaction is observed. To ensure close monitoring, participants will remain in or close to their bed for at least 6 hours after completion of the infusion.

LY3832479 Dose (mg)	Volume withdraw from DP vial (mL)	Volume of sterile diluent (mL)	Total infusion volume (mL)	Start infusion rate(duration)
700	17.5	32.5	50	100 mL/h (30 min, allowable range 25 - 60 min)
2800	70	None	70	100 mL/h (42 min, allowable range 37 – 75 min)
7000	175	None	175	100 mL/h (105 min, allowable range 100 - 150 min)

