6.3. Measures to Minimize Bias: Randomization and Blinding

Randomization tables for allocation of either LY3832479 or placebo will be prepared by the statistician or their designee.

Blinding will be maintained throughout the conduct of the study as described in the separate Blinding Plan.

Emergency codes will be available to the investigator. A code, which reveals the treatment group for a specific study subject, may be opened during the study only if the subject's well-being requires knowledge of the subject's treatment assignment.

In case of an emergency, the investigator has the sole responsibility for determining if unblinding of a subject's treatment assignment is warranted for medical management of the event. The subject's safety must always be the first consideration in making such a determination. If the investigator decides that unblinding is warranted, it is the responsibility of the investigator to promptly document the decision and rationale and notify Lilly as soon as possible.

If an investigator, site personnel performing assessments, or participant is unblinded while the infusion is ongoing, the participant must be discontinued from the study intervention and the infusion stopped. If any amount of study intervention was administered, follow procedures according to the SoA as described in Section 7.1.

Upon completion of the study, all codes must be returned to Lilly or its designee.

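### The dose-proportionality model has no body-weight term; a prespecified weight-adjusted second fit would be a cheap improvement if weight affects exposure

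*SAP*

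**What the plan says.** SAP 9.3.2 evaluates dose proportionality for log Cmax and log AUC(0-∞). Each "will be evaluated using a power model (where log-dose acts as an explanatory variable", giving ratios of dose-normalised geometric means and "corresponding 90% confidence intervals". The sample code agrees with the text: "model log_pk = log_dose / alpha=0.1 cl solution residual ddfm=kr". The quantity of interest is the top-to-bottom comparison: "The estimated ratio of dose-normalized geometric means of PK parameters between the highest and lowest doses will be used to assess dose proportionality". No acceptance range is given.

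Doses are flat amounts in mg (Protocol 6.1, starting with "Cohort 1: 700 mg", then 2800 mg and 7000 mg). Protocol 4.1.1 plans at least 7, 7 and 6 active participants in successive cohorts. Randomisation concerns only active drug against placebo: "Randomization tables for allocation of either LY3832479 or placebo will be prepared by the statistician or their designee" (Protocol 6.3). Entry limits BMI (Protocol 5.1) but not weight.

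Weight is measured at screening (Protocol 1.3). SAP 9.2 uses it descriptively: "The demographic variables age, sex, race, ethnicity, body weight, height and body mass index will be summarized and listed". Protocol 9.4.5.2 has baseline characteristics summarised by treatment group, and SAP 6 lists the three dose levels as separate treatments.

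**The concern.** Dose level is the explanatory variable in the only inferential analysis that the SAP specifies, yet nobody is randomised to a dose level. With flat dosing, a heavier participant gets less drug per kilogram. If clearance or volume rises with weight, that participant has lower exposure for a reason unrelated to dose. The model has no term for this, so the effect can surface in two places.

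- **Residual:** weight variation among participants on the same dose is left as unexplained scatter and widens the interval.
- **Slope:** if one cohort happens to be heavier than another, the difference moves the 7000:700 mg ratio.

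At stake is how the proportionality ratio is read. Someone who sees a weight imbalance in the demographic table would have no prespecified way to separate weight from dose, and an adjustment chosen at that stage would be post hoc.

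**Working it through.** Neither document gives a precision calculation for dose proportionality, so there is no planned figure to reproduce.

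**From the documents.** Doses 700, 2800 and 7000 mg; active n = 7, 7, 6; two-sided 90% interval; highest-to-lowest dose ratio 10, with ln 10 = 2.303. (The contrast in the sample code is 0.97003679 in base-10 logs, a 9.33-fold range. That is a separate matter, and the true 10-fold range is used here.)

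**Assumed, not in the documents.** ln(PK) = constant + ln(dose) − k·ln(weight) + error, with k from 0.5 to 1.0 (0 as a check), weight CV 15% to 20% and remaining PK CV 15% to 30%. On the log scale SD = √ln(1+CV²), which gives 0.149 to 0.198 and 0.149 to 0.294.

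**1. Design.** Mean ln(dose) = 7.727. Sxx = 7(−1.176)² + 7(0.210)² + 6(1.127)² = 9.68 + 0.31 + 7.62 = 17.61. The multiplier from slope to log ratio is ln 10/√17.61 = 0.549.

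**2. Interval width (within-cohort variation).** Half-width on the log scale = t × s × 0.549. Without weight, s² = k²σ²(weight) + σ²(other), on 18 df (t = 1.734). With weight, s² = σ²(other), on 17 df (t = 1.740), plus a small loss from chance correlation between weight and dose.

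At k = 0.75 and both CVs 20%:
- unadjusted: s = √(0.75² × 0.198² + 0.198²) = 0.248, so 1.734 × 0.248 × 0.549 = 0.236 (simulated mean 0.233)
- adjusted: 1.740 × 0.198 × 0.549 = 0.189 before the correlation loss (simulated mean 0.192)

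Simulated mean half-widths, 4,000 trials per row, no weight drift:

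| k | Weight CV | Other CV | Without weight | With weight | Factor |
|---|---|---|---|---|---|
| 0 | 18% | 25% | 0.231 | 0.239 | 1.03 |
| 0.5 | 15% | 30% | 0.283 | 0.283 | 1.00 |
| 0.5 | 20% | 20% | 0.207 | 0.191 | 0.92 |
| 0.75 | 20% | 20% | 0.233 | 0.192 | 0.82 |
| 1.0 | 20% | 20% | 0.262 | 0.192 | 0.73 |
| 1.0 | 20% | 15% | 0.233 | 0.145 | 0.62 |

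In the second row the adjusted interval is the wider one in 59% of trials.

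**3. Shift of the ratio (between-cohort difference).** Suppose PK is truly proportional and only the 7000 mg cohort is 10% heavier. The slope moves by −k × 6 × 1.127 × ln(1.1)/17.61 = −0.0366k. The ratio becomes exp(−0.0366 × 2.303 × k) = exp(−0.0843k), which is 0.96, 0.94 and 0.92 for k = 0.5, 0.75 and 1.0. If weight instead rises steadily with log dose to 10% at the top, the ratio is 1.1^(−k) = 0.95, 0.93 and 0.91.

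**4. Coverage of the nominal 90% interval.**
- Systematic, 7000 mg cohort 10% heavier (k = 0.75, log SDs 0.19 for weight and 0.20 for the rest): about 86% to 87% unadjusted, 90% adjusted.
- Systematic steady 10% drift (weight CV 18%, other CV 20%): 87% at k = 0.5 and 84% at k = 1.0 unadjusted; 90% and 92% adjusted.
- No drift: the unadjusted estimate is unbiased and coverage is 89% to 91%. At weight CV 18% the chance high-to-low weight ratio has log SD 0.179 × 0.549 = 0.098, so its 90% range is ×/÷ exp(1.645 × 0.098) = 1.17. The interval already carries this variation.
- No drift, but looking only at trials with a large realised imbalance (log SDs 0.19 and 0.20): about 18% of trials show a weight ratio at least 15% away from 1. Among those, unadjusted coverage is 83%, 76% and 71% for k = 0.5, 0.75 and 1.0. At 8% to 12% imbalance it stays at about 91%.

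The adjusted model performs well here partly because the data were generated from it.

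**The case against.** The strongest reply is that harm is inferred from inputs that the documents do not supply. No weight effect on PK is quantified, all cohorts share the same entry criteria, and nothing suggests that later cohorts will be heavier. Without such a drift the planned analysis is valid over repeated trials. This stands, and it limits the point.

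A reader might also take Table 4.1, with its footnote "Assume 70-kg bodyweight", and the allometric half-life projection in Protocol 4.3 as an admission that exposure depends on weight. They do not show that. Both translate between monkey and human, and say nothing about variation among adults.

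The remaining replies also carry weight. An imbalance would be visible, because weight will be tabulated by dose group. The SAP allows supplementary analyses (SAP 3), and the protocol allows a compartmental analysis (Protocol 9.4.3). The study is exploratory and PK is secondary. Escalation is guided primarily by safety and tolerability, and no proportionality limit is set. At k = 0.75, a ratio of 0.94 with log half-width 0.230 spans about 0.75 to 1.18, which still includes 1. An exponent estimated from about 20 people is imprecise, which argues against displacing the planned model.

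What these replies do not provide is a prespecified adjusted estimate. A table shows an imbalance but does not say what it does to the ratio, and neither optional analysis mentions weight.

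**Conclusion.** The point holds as a conditional, low-cost improvement to a secondary analysis. The planned model omits a baseline variable that is already collected, in a comparison that randomisation does not protect.

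If the weight exponent lies between 0.5 and 1.0, adjustment multiplies the half-width by about 0.62 to 1.00 over the assumed range of variability. The gain is nil at the weak-effect, noisy-PK end. A 10% heavier top cohort would move the ratio to about 0.94 at exponent 0.75.

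A reader might infer that the planned ratio is biased, or that weight differences will be read as dose effects in this trial. The documents do not support that. Bias and under-coverage over repeated trials need a systematic drift of weight with cohort, for which there is no evidence. Nor do between-cohort differences and interval width form one problem: the first shifts the ratio, while within-cohort variation widens the interval. All sizes rest on the assumed exponent and variances.

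**What to change.** In SAP 9.3.2, prespecify a second fit for both Cmax and AUC(0-∞): `model log_pk = log_dose log_wt`, where `log_wt` is log screening weight minus log(70 kg), in the same log base as dose. Centring at the 70 kg that the protocol uses in Table 4.1 makes the dose-level estimates refer to a 70-kg participant. Report the weight-adjusted highest-versus-lowest-dose ratio with its 90% interval beside the planned result, whatever imbalance is seen. The log-dose-only fit may remain the main analysis.

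The cost is one sentence, one model term and 1 of 18 residual degrees of freedom, with no new data. If weight is irrelevant, the adjusted interval is about 3% wider than the planned one.
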